Patients treated with doses of tremelimumab above 1 mg/kg had a higher rate of adverse events (AEs), including discontinuations due to AEs, serious AEs (SAEs), and severe AEs. Between the 10 mg/kg durvalumab + 1 mg/kg tremelimumab and 10 mg/kg durvalumab + 3 mg/kg tremelimumab cohorts treated at the q2w schedule, the number of patients reporting any AE, grade 3 AEs, SAEs, and treatment-related AEs was higher in the 10 mg/kg durvalumab + 3 mg/kg tremelimumab cohort than the 10 mg/kg durvalumab + 1 mg/kg tremelimumab cohort. A similar pattern was noted in the q4w regimens, suggesting that, as the dose of tremelimumab increased above 1 mg/kg, a higher rate of treatment-related events may be anticipated. Further, the SAEs frequently attributed to immunotherapy, pneumonitis and colitis, were more commonly seen in cohorts using either 3 or 10 mg/kg of tremelimumab compared to the 1-mg/kg dose cohorts. Together, these data suggest that a combination using a tremelimumab dose of 1 mg/kg appeared to minimize the rate of toxicity when combined with durvalumab. As a result, all combination doses utilizing either the 3 or 10 mg/kg doses of tremelimumab were eliminated in the final dose selection.

In contrast, cohorts assessing higher doses of durvalumab with a constant dose of tremelimumab did not show an increase in the rate of AEs. The data suggested that increasing doses of durvalumab may not impact the safety of the combination as much as the tremelimumab dose. Further, safety data between the 10-mg/kg and 20-mg/kg cohorts were similar, with no change in safety events with increasing dose of durvalumab.

In Study D4190C00006, of all treatment cohorts, the cohort of 11 patients treated in the 20 mg/kg durvalumab + 1 mg/kg tremelimumab group had the fewest AEs, Grade  $\geq 3$  AEs, SAEs, and treatment discontinuations due to AEs, but still showed strong evidence of clinical activity. This cohort had a lower number of treatment-related Grade  $\geq 3$  AEs or treatment related SAEs. No dose-limiting toxicities were reported.

Preliminary clinical activity of the durvalumab and tremelimumab combination did not appear to change with increasing doses of tremelimumab. The 15- and 20-mg/kg durvalumab q4w cohorts demonstrated objective responses at all doses of tremelimumab and increasing doses of tremelimumab did not provide deeper or more rapid responses.

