#### 1.2.10 Current status of 13-C-0120 and rationale for this new protocol (as of March 11, 2016).

The current status of NCI 13-C-0120 is as follows. We began enrollment on July 24th, 2013. In total, N=41 patients have been enrolled across 4 cohorts as shown (N=32 with HCC; N=9 with cholangiocarcinoma). Of the N=32 patients with HCC, N=4 have been unevaluable, having come off study treatment for either toxicity or disease progression within the first few weeks of treatment. Treatment overall has been well tolerated. No DLT was encountered at an initial mini dose escalation of 3.5mg/kg so we proceeded to the recommended tremelimumab dose of 10mg/kg. Most common toxicity was grade 1/2 pruritus. One patient developed pneumonitis and was taken off study but remained disease-free at 16m. In total n=3 patients discontinued therapy due to immune-related adverse events (pneumonitis, colitis, adrenal insufficiency) which is consistent with what would be expected from single-agent immune checkpoint experience. We have also seen evidence of efficacy with a PR rate of 23.5% and prolonged stability (>6 months) in an additional 23.5%. Given the context of HCC – generally a poorly responsive tumor type – these results are encouraging.

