The field has moved on a little given the recently presented data showing highly encouraging and dramatic results for nivolumab (anti-PD1 therapy) in HCC. Based on this it is likely that nivolumab will challenge the status of sorafenib as the front-line (and only) option for this disease. Randomized trials are ongoing. Even if this occurs however, and while complete responses were seen in the nivolumab study, the majority of patients did not seem to derive benefit. The current research focus of the field is on combinations, either of two different immunotherapies or immunotherapy combined with non-immunotherapy. One of the striking things that we have seen in our own study so far is that anti-CTLA4 therapy (with tremelimumab) is capable of driving T-cell infiltration into the tumor[32]. In actual fact, based on further analysis that we have performed[33] it appears that this occurrence is a prerequisite for response to tremelimumab in HCC. However, the concept of PDL1-mediated ‘adaptive resistance’ – i.e. resistance emerging due to PDL1 upregulation secondary to interferon-gamma – means that responses are destined to be short-lived. This has been our experience, with only one of our 5 PRs lasting longer than one year. Conversely, combined immune checkpoint inhibition, with the addition of anti-PD1/PDL1 therapy can overcome this and has demonstrated increased

clinical response rates in melanoma. We would therefore like to open new cohorts which combine anti-PDL1 therapy (durvalumab) with anti-CTLA4 (tremelimumab).

The combination of tremelimumab and durvalumab has been tested in a dose-escalation study performed by AstraZeneca employing dose ranges of 1-10mg/kg q4weeks (tremelimumab) and 10-20mg/kg q2-4weeks (durvalumab). Patients treated in the 20 mg/kg durvalumab + 1 mg/kg tremelimumab group had the fewest AEs, Grade  $\geq 3$  AEs, SAEs, and treatment discontinuations due to AEs, but still showed strong evidence of clinical activity. This cohort had a lower number of treatment-related Grade  $\geq 3$  AEs or treatment related SAEs. No dose-limiting toxicities were reported. This is the dose level the company is bringing forward. Also, of note, PK analysis indicated only minor impact of body weight (WT) on PK of both agents so to minimize errors and for ease of use the company have moved to a fixed-dose schedule of 1500 mg Q4W durvalumab (equivalent to 20 mg/kg Q4W) and 75 mg Q4W tremelimumab (equivalent to 1 mg/kg Q4W).

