### 3 STUDY IMPLEMENTATION

#### 3.1 STUDY DESIGN

The proposed study is a pilot study combining tremelimumab and durvalumab treatment in patients with advanced HCC (Cohorts A1 and A2) either alone (Arm A1) or with cryoablation, TACE or RFA (Arms A2, A3, A4) and patients with advanced BTC (Cohort B) either alone (Arm A1) or with cryoablation or RFA (Arms A3, A4).

The decision on which interventional radiologic procedure to administer (i.e. RFA vs. TACE vs. cryoablation) will be made in consultation with the interventional radiologists. The reason for this is that there are technical considerations (size and location of lesion, main portal vein occlusion etc.) which would make one procedure preferable over the other.

- Transarterial chemoembolization is percutaneous procedure performed under general anesthesia or conscious sedation. (See 3.5.1 for details)
- Patients undergoing trans-arterial chemoembolization, RFA or cryoablation are pre-medicated with analgesics, antibiotics and anti-emetics per clinical standards. For details regarding each procedure please see 3.5.

Cohort	Population	Immune stimulating procedure	Dose level	Planned N
A1	Advanced HCC, BCLC Stage C	No ablative procedure	Tremelimumab 75mg flat dose q28 days for 4 doses Durvalumab 1500mg flat dose q28 days until EOS###	10 total
A2	Advanced HCC, BCLC Stage B/C	Cryoablation/ RFA/TACE*	Tremelimumab 75mg flat dose q28 days for 4 doses Durvalumab 1500mg flat dose q28 days until EOS**	30 total 10 trem+ dur + TACE 10 trem + dur + RFA 10 trem + dur + cryo
B	Intra/extra-hepatic cholangiocarcinoma	N= 1st 10 pts: No ablative procedure  RFA/ cryoablation	Tremelimumab 75mg flat dose q28 days for 4 doses Durvalumab 1500mg flat dose q28 days until EOS**	30 total 10 trem+ dur alone 10 trem + dur + RFA 10 trem + dur + cryo

\* For BCLC stage B patients TACE may be repeated as per standard of care

\*\* EOS = end of study treatment as defined in section 3.8.1.

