### **3.2 SCHEDULE**

#### **3.2.1 Cohort A1**

- All 10 patients with BCLC Stage C will receive combined immune checkpoint inhibition only i.e. no interventional radiologic procedure.
- Patients will receive 1500 mg durvalumab via IV infusion q4w for up to 4 doses/cycles and 75 mg tremelimumab via IV infusion q4w for up to 4 doses/cycles, and then continue 1500 mg durvalumab q4w. Tremelimumab will be administered first. Durvalumab infusion will start approximately 1 hour after the end of tremelimumab infusion. The duration will be approximately 1 hour for each infusion. A 1-hour observation period is required after the first infusion of durvalumab and tremelimumab. If no clinically significant infusion reactions are observed during or after the first cycle, subsequent infusion observation periods can be at the Investigator's discretion (suggested 30 minutes after each durvalumab and tremelimumab infusion).

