Pharmacokinetic studies m		X	X n	X n		X				X				X						X
Immunogenicity t		X				X				X				X						X s
AMA & Liver/kidney microsomal antibody q	X													X						
Tumor-specific αFP responses q		X				X								X						X s
CFSE		X				X								X						X s

Procedure	Pre-study	Cycle 1				Cycle 2				Cycle 3				Cycle 4				D1 of every subsequent cycle 0	EOT P	LT FU r
		1	8	15	22	1	8 (day 36)	15	22	1	8	15	22	1 (day 85)	8	15	22			
Day		1	8	15	22	1	8 (day 36)	15	22	1	8	15	22	1 (day 85)	8	15	22			
proliferation T cells q																				
MDSC functional assay q		X				X				X				X						
T cell activation/ICOS expression (PBMC) t		X	X n	X n		X				X				X						
Plasma-based assays for circulating receptors/ligands e.g. PDL1 t		X				X	X n			X	X n			X						
Rectal swab (optional)	X					X								X						
Phone call or e-mail																		X	X	

- a. Tremelimumab: flat dose of 75 mg q4wk (+/- 7 days) for 4 doses only. Durvalumab: flat dose of 1500 mg q4wk (+/- 7 days).
- b. RFA/TACE/cryoablation on day 36 +/- 96 hrs.
- c. Filling out of the Advance Directive Form will be offered but obtaining of it is not required. This should be done preferably at baseline but can be done at any time during the study as long as the capacity to do so is retained. For details see Section 12.4.

- d. Full physical examination at screening; targeted physical examination at other time points
- e. within 30 minutes before and within 30 minutes after infusion.
- f. If pre-study laboratory assessments are performed within 3 days prior to Day 1 they do not need to be repeated at Day 1. Results for safety bloods must be available and reviewed before commencing an infusion. For all labs, a ‘+/- 72 hr’ window applies, with the exception of those needed to determine proceeding with treatment. Labs may be performed outside of NIH.
- g. Biochemical profile: electrolytes, BUN, creatinine, AST, ALT, total and direct bilirubin, calcium, phosphorus, albumin, magnesium.
- h. Free T3 and free T4 will only be measured if TSH is abnormal. They should also be measured if there is clinical suspicion of an adverse event related to the endocrine system.
- i. Screening, Day 1 and during the study, but only if clinically indicated

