#### 14.1.3 Administration Procedures

Tremelimumab is to be administered as an IV solution of 10 mg/kg at a rate of 250 mL/hr, followed by observation for 60 minutes.

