#### 14.1.4 Dose Calculation

**Note:** The dosing for tremelimumab will be a flat dosing of 75 mg.

The corresponding volume of investigational product should be rounded to the nearest tenth of a mL (0.1 mL). Each vial contains a small amount of overage and the overage should be utilized as much as possible before using another vial.

The number of vials required for dose preparation is the next greatest whole number of vials from the following formula:  $\text{Number of vials} = \text{Dose (mL)} \div 20 \text{ (mL/vial)}$

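### Section 14.1.3 orders tremelimumab at 10 mg/kg, while every other dosing instruction in the protocol gives a flat 75 mg

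*Combined protocol and SAP*

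**What the plan says.** The tremelimumab dose appears in these operative places:

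- Section 14.1.3 (Administration Procedures): "Tremelimumab is to be administered as an IV solution of 10 mg/kg at a rate of 250 mL/hr". No cohort, arm or weight band limits the instruction.
- Section 14.1.4 (Dose Calculation): "The dosing for tremelimumab will be a flat dosing of 75 mg".
- Section 3.1, design table, for cohorts A1, A2 and B: "Tremelimumab 75mg flat dose q28 days for 4 doses".
- Section 3.2.1, repeated in 3.2.2 and 3.2.3: "75 mg tremelimumab via IV infusion q4w for up to 4 doses/cycles".
- Section 3.6, footnote a: "Tremelimumab: flat dose of 75 mg q4wk (+/- 7 days) for 4 doses only". The calendar grid shows dosing days only and gives no dose.

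The background explains both numbers. Section 1.2.10 describes the flat dose as "75 mg Q4W tremelimumab (equivalent to 1 mg/kg Q4W". In the same section, the account of the predecessor study (13-C-0120) reads: "so we proceeded to the recommended tremelimumab dose of 10mg/kg". Section 1.2.6.1, on the dose-escalation study of the combination, says that "all combination doses utilizing either the 3 or 10 mg/kg doses of tremelimumab were eliminated in the final dose selection".

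**The concern.** Section 14.1.3 is a current instruction on how to give the drug, neither background nor an amendment history, and its dose conflicts with the rest of the protocol. The figure matches the predecessor study's dose, so it looks like text carried over from that protocol. The documents do not say so, and this remains an inference.

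Patient safety is at stake. Section 1.2.6.1 reports more adverse events, serious adverse events and discontinuations above 1 mg/kg, with pneumonitis and colitis commoner at 3 or 10 mg/kg. The trial admits patients with cirrhosis up to Child-Pugh B7 (2.1.1.6), and 12.5.1.2 lists hepatitis that can in extreme cases be fatal among the tremelimumab risks. Section 8.5.2.1 says there is no specific treatment for overdose and requires any overdose to be reported within 24 hours, which presupposes a single unambiguous reference dose.

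**Working it through.** **Inputs**

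- Dose in 14.1.3: 10 mg/kg.
- Dose in 14.1.4, 3.1, 3.2.1 to 3.2.3 and 3.6 footnote a: 75 mg flat.
- Stated equivalences (1.2.10): tremelimumab 75 mg = 1 mg/kg; durvalumab 1500 mg = 20 mg/kg.
- Eligibility: body weight above 30 kg (2.1.1.13).
- Tremelimumab: 20 mg/mL, in vials of 20.0 mL (400 mg) or 1.25 mL (25 mg) (14.1.2).
- Durvalumab: 50 mg/mL, in 10 mL vials (14.2.2).
- Body weights other than the 30 kg limit and the implied 75 kg are assumptions, used to show a range.

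**Step 1. Reproduce the plan's own equivalence.** Reference weight = flat dose / dose per kg. Tremelimumab: 75 / 1 = 75 kg. Durvalumab: 1500 / 20 = 75 kg. The two agree, so 75 mg as 1 mg/kg is internally sound.

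**Step 2. Can the two instructions be reconciled?** They coincide only at 75 mg / (10 mg/kg) = 7.5 kg, which eligibility rules out.

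**Step 3. Size of the discrepancy.** Dose under 14.1.3 = 10 × weight; ratio = that dose / 75; volume = dose / 20 mg/mL.

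| Weight | Dose under 14.1.3 | Ratio to 75 mg | Volume |
|---|---|---|---|
| 30 kg (eligibility limit) | 300 mg | 4.0 | 15.0 mL |
| 50 kg (assumed) | 500 mg | 6.7 | 25.0 mL |
| 70 kg (assumed) | 700 mg | 9.3 | 35.0 mL |
| 75 kg (implied reference) | 750 mg | 10.0 | 37.5 mL |
| 100 kg (assumed) | 1000 mg | 13.3 | 50.0 mL |

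The intended dose is 75 / 20 = 3.75 mL.

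**Step 4. Would other text catch the error?**

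- Section 3.3.1, the other tremelimumab administration section, gives rate, volume and filter but no dose in mg. Its 250 mL/hour agrees with 14.1.3, so only the dose in that sentence is wrong.
- Section 14.1.6 tells staff to calculate the dose volume and gives no fixed volume. Durvalumab has one: 30.0 mL, in 14.2.3.
- The vial formula in 14.1.4 raises no flag. At an assumed 70 kg, 35 / 20 = 1.75, which rounds up to an unremarkable two 400-mg vials.

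**Step 5. Vial-count divisors (minor, separate from the safety point).** Both 14.1.4 and 14.2.4 divide the dose volume by 20 mL per vial and round up.

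- Durvalumab: 1500 / 50 = 30 mL. The formula gives 30 / 20 = 1.5, so 2 vials; 10 mL vials require 30 / 10 = 3.
- Tremelimumab, 400-mg vial: 3.75 / 20 rounds up to 1, which is correct.
- Tremelimumab, 25-mg vial: the formula again gives 1, but 3.75 / 1.25 = 3 are needed. If the volume is first rounded to 3.8 mL under the 0.1 mL rule in 14.1.4, then 3.8 / 1.25 = 3.04, which would round up to 4. That section's instruction to use vial overage before opening another vial points to 3.

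These are errors in counting vials, not stated underdoses: vial numbers are assigned by IXRS, and the dose is added to the bag by calculated volume (14.1.6, 14.2.5).

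**The case against.** The strongest reply is that no careful reader would be misled. The subsection devoted to dose calculation comes directly after the faulty sentence and opens with the flat 75 mg. Every schedule agrees with it, and IXRS assigns the vials. On that view this is a clerical slip. These safeguards do lower the risk, but they do not correct an unqualified instruction to administer 10 mg/kg, and the documents do not say which dose IXRS is programmed to supply.

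A second reply limits the safety evidence. The rejection of 3 and 10 mg/kg comes from a phase Ib study in advanced NSCLC (1.2.6.1), not in HCC or BTC, and 1.2.10 describes treatment in the predecessor study, which gave tremelimumab without durvalumab, as well tolerated overall. This stands as a limit on the claim: the documents show a dose rejected for the combination in another population, not measured harm in these patients. It does not rescue 14.1.3, because this trial took its combination dose from that NSCLC study.

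It is also fair to say that the vial-count errors are a different and lesser defect. They carry none of the safety argument.

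**Conclusion.** The concern holds: the dose in 14.1.3 is wrong as written and must be corrected. It is ten times the intended level in mg/kg terms. Against the 75 mg flat dose the excess is 4.0-fold at the 30 kg eligibility limit, rising to 13.3-fold at an assumed 100 kg. The conclusion itself does not depend on the assumed weights, since no eligible weight reconciles the two doses. It rests on taking 75 mg as the governing dose, which the consistent text elsewhere and the rationale in 1.2.10 support. The finding concerns the text, not conduct of the trial. The incorrect vial divisors are confirmed as a minor, secondary point.

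**What to change.** In 14.1.3, replace 10 mg/kg with 75 mg (flat dose), leaving the infusion rate and observation period unchanged.

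In the same amendment, as minor corrections:

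- In 14.2.4, change the divisor to 10 mL per vial, giving 3 vials for 30 mL.
- In 14.1.4, give the divisor by vial size: 20 mL for the 400-mg vial (1 vial) and 1.25 mL for the 25-mg vial. State explicitly that 3 of the 25-mg vials are used for 3.75 mL, so that rounding to 3.8 mL does not call for a fourth.

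The cost is a text amendment and a pharmacy memo. Sample size, power and the analysis do not change.

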#### 14.1.4 Dose Calculation

**Note:** The dosing for tremelimumab will be a flat dosing of 75 mg.

The corresponding volume of investigational product should be rounded to the nearest tenth of a mL (0.1 mL). Each vial contains a small amount of overage and the overage should be utilized as much as possible before using another vial.

The number of vials required for dose preparation is the next greatest whole number of vials from the following formula:  $\text{Number of vials} = \text{Dose (mL)} \div 20 \text{ (mL/vial)}$

#### 14.1.5 Investigational Product Inspection

Each vial selected for dose preparation should be inspected.

If there are any defects noted with the investigational product, the investigator and site monitor should be notified immediately. Refer to the Product Complaint section ([14.1.8](#)) for further instructions.

During the inspection if the solution is not clear or any turbidity, discoloration or particulates are observed, notify your site monitor and store the vial(s) in QUARANTINE at refrigerated (2-8°C) temperature for drug accountability and potential future inspection.

Notify the IXRS that the unusable vials are damaged. The IXRS will indicate the replacement vials. Select appropriate replacement vials for the preparation of the subject's dose and perform the same inspection on the newly selected vials. For accountability, record the total number of vials removed from site inventory. Used vials should be held for accountability purposes at ambient storage temperature.

#### 14.1.6 Dose Preparation Steps

Tremelimumab does not contain preservatives and any unused portion must be discarded. Preparation of tremelimumab and preparation of the IV bag are to be performed aseptically. Total in-use storage time for the prepared final IV bag should not exceed 24 hours at 2-8°C or 4 hours at room temperature (25°C). However, it is recommended that the prepared final IV bag be stored in the dark at 2-8°C until needed. The refrigerated infusion solutions in the prepared final IV bag should be equilibrated at room temperature for about 2 hours prior to administration. If storage time exceeds these limits, a new dose must be prepared from new vials.

The investigational product manager or qualified personnel will be responsible for preparing the IV doses using the following steps:

1) Select the IXRS-assigned number of vials of investigational product required to prepare the subject's dose.

2) All investigational product vials should be equilibrated to room temperature for 30 minutes prior to dose preparation.

3) To prepare the IV bag, first, calculate the dose volume of investigational product required. Second, remove the volume of 0.9% sodium chloride IV solution equivalent to the calculated dose volume of investigational product from the IV bag. Lastly, add the calculated dose volume of investigational product to the IV bag. Gently mix the solution in the bag by inverting up and down. Avoid shaking the IV bag to prevent foaming.

Labels will be prepared in accordance with Good Manufacturing Practice (GMP).

#### 14.1.7 Investigational Product Accountability

The investigator's or site's designated investigational product manager is required to maintain accurate investigational product accountability records. Upon completion of the study, copies of investigational product accountability records will be returned to MedImmune. All unused investigational product will be returned to a MedImmune-authorized depot or disposed of upon authorization by MedImmune.

#### 14.1.8 Reporting Product Complaints

Any defects with the investigational product must be reported *immediately* to the MedImmune Product Complaint Department by the site with further notification to the site monitor. All defects will be communicated to MedImmune and investigated further with the Product Complaint Department. During the investigation of the product complaint, all investigational products must be stored at labeled conditions unless otherwise instructed.

Product defects may be related to component, product, or packaging and labeling issues. The list below includes, but is not limited to, descriptions of product complaints that should be reported.

**Component Issue:** Defect in container or dosing mechanism of the investigational product. The component defect may be damaged, missing, or broken. Component examples include vials, stoppers, caps, spray barrels, spray nozzles, or plungers.

**Product Issue:** Defect in the product itself. The product appearance has visual imperfections such as foreign particles, crystallization, discoloration, turbidity, insufficient volume, or anything that does not apply to the product description.

**Packaging/Labeling Issue:** Defect in the packaging or labeling of the product. The packaging or labeling defects may be damaged or unreadable, or the label may be missing.

When reporting a product complaint, site staff must be prepared to provide the following information:

- 1) Customer information: reporter name, address, contact number, and date of complaint
- 2) Product information: product name, packaging kit number or lot number, expiry date, and clinical protocol number
- 3) Complaint information: complaint issue category and description

MedImmune contact information for reporting product complaints:

Email: [[contact]](mailto:[contact])

[contact] [name] ([contact])  
[contact]

Mail: MedImmune, LLC Attn: Product Complaint Department [name],  
[name]

